# 16.1.1.2 Dried Blood Spot Assay

Concentrations of M5717 in DBS samples will be measured at selected time points in Part C cohorts.

Concentration values below the LLOQ of the assay will be taken as zero for summary statistics of DBS PK concentration data.

### 16.1.1.3 Urine and Feces

Daily 24-hour urine and feces may be collected in male subjects only in one of the cohorts in Part A during the residential period (up to Day 7), and urine may be collected during the ambulant periods (24-hour collections around Day 15, Day 22, Day 33, and Day 44). Urine and fecal concentrations for M5717 and/or metabolites, if available, will be reported in a separate report.

# 16.1.2 Derivation of Individual Whole Blood, Urine, and Fecal Pharmacokinetic Parameters

### 16.1.2.1 Whole Blood

Pharmacokinetic parameters will be calculated b PPD using standard non-compartmental methods and the actual administered dose. PK parameters will be calculated using the actual

elapsed time since dosing, given with a precision of 14 significant digits. In cases where the actual sampling time is missing, calculations will be performed using the nominal time. Otherwise, there will be no further imputation of missing data.

The following parameters will be calculated from M5717 whole blood concentrations in Part A and Part C. If M5717 whole blood metabolite concentrations are available in Part A, parameters may also be calculated for these metabolites (if applicable, and if sufficient data are available).

| Symbol                         | Definition  |
|--------------------------------|---|
| AUC 0-t             | The AUC from time zero (= dosing time) to the last sampling time (t last ) at which the concentration is at or above the lower limit of quantification. Calculated using the mixed log linear trapezoidal rule (linear up, log down).  |
| AUC 0-t /Dose       | The dose-normalized $AUC_{0-t}$ . Normalized using the actual dose, using the formula $AUC_{0-t}/Dose$ .  |
| AUC 0-144h          | The AUC from time zero (= dosing time) to 144 hours postdose. Calculated using the mixed log linear trapezoidal rule (linear up, log down).   |
| AUC 0-144h
/Dose | The dose-normalized AUC $_{0-144h}$ . Normalized using the actual dose, using the formula AUC $_{0-144h}$ /Dose.  |
| AUC 0-∞             | The AUC from time zero (dosing time) extrapolated to infinity, based on the predicted value for the concentration at $t_{last}$ , and estimated using the linear regression from the determination of the terminal first order (elimination) rate constant ( $\lambda_z$ ). AUC 0-<math>\infty</math> = AUC 0-<math>\tau</math> +C last pred / $\lambda_z$ . |
| AUC 0-∞ /Dose       | The dose-normalized AUC0- $\infty$ . Normalized using actual dose, using the formula AUC0- $\infty$ /Dose.  |
| AUC extra %         | The AUC from time $t_{last}$ extrapolated to infinity given as percentage of AUC 0-<math>\infty</math> . AUC extra % = (extrapolated area/AUC 0-<math>\infty</math> )*100.   |
| $\mathrm{CL}_{\mathrm{f}}$     | The apparent total body clearance of drug following extravascular administration, taking into account the fraction of dose absorbed. $CL/f = Dose /AUC_{0-\infty}$ . Calculated for M5717 only.   |
| $C_{max}$                      | Maximum observed concentration.   |

24/31

| Symbol                    | Definition  |
|---------------------------|---|
| C max
/Dose | The dose-normalized $C_{\text{max}}$ . Normalized using the actual dose, and the formula $C_{\text{max}}/\text{Dose}$ .   |
| $\lambda_z$               | Terminal first order (elimination) rate constant. Determined from the terminal slope of the log-transformed concentration curve using linear regression on terminal data points of the curve.   |
| t 1/2          | Apparent terminal half-life. $t_{1/2} = \ln (2)/\lambda_z$ .  |
| t max          | The time to reach the maximum observed concentration collected during a dosing interval (in case of multiple/identical C max values, the first occurrence will be used).   |
| $V_{\mathrm{Z/f}}$        | The apparent volume of distribution during the terminal phase following extravascular administration, based on the fraction of dose absorbed. $V_{z/f} = Dose/(AUC_{0-\infty}*\lambda_z)$ following single dose. Calculated for M5717 only. |
| t>3 ng/mL                 | Time above or equal to the predicted M5717 mouse minimum inhibitory concentration (MIC) of 3 ng/mL.   |
| t>10 ng/mL                | Time above or equal to the predicted M5717 mouse minimal parasiticidal concentration (MPC) of 10 ng/mL.   |

For  $CL_{\rm ff}$  and  $V_{\rm Z/f}$  and all dose-normalized parameters, the actual M5717 dose after adjustment for molecular weight differences between salt and free base form will be used for calculation of these parameters (ie, Adjusted dose = Dose \* 462.56/580.65), where 462.56 and 580.65 are the molecular weights of the M5717 free base and succinate salt, respectively.

The following PK parameters will be calculated for diagnostic purposes and listed for Part A and Part C, but will not be summarized:

- The time interval (h) of the log-linear regression (λz low, λz upp) to determine λz.
- Number of data points (Nλ) included in the log-linear regression analysis to determine λz.
- Goodness of fit statistic (Rsq) for calculation of λz.

The regression analysis for  $\lambda_z$  should contain data from at least 3 different time points in the terminal phase consistent with the assessment of a straight line on the log-transformed scale. Phoenix WinNonlin best fit methodology will be used as standard. However, in some cases, further adjustment may be made by the pharmacokineticist, if warranted, after agreement from the Sponsor. The last quantifiable concentration should always be included in the regression analysis, while the concentration at  $t_{max}$  and any concentrations below the LLOQ which occur after the last quantifiable data point should not be used.

The Rsq should be  $\geq$ 0.800 and the observation period over which the regression line is estimated should be at least two-fold the resulting  $t_{1/2}$  itself. If these criteria are not met, then the rate constants and all derived parameters will be included in the parameter outputs and descriptive statistics but will be flagged and discussed appropriately. The AUCextra% should be less than 20.0%. If this criterion is not met, AUC0. $\infty$  and all derived parameters will be included in the parameter outputs and descriptive statistics but will be flagged and discussed appropriately. Any flags should be included in the study specific SDTM.

Partial areas should be calculated using the nominal dosing interval, as defined in the clinical trial protocol. The actual dosing interval calculated from case report form (CRF) time data should not be used.

Concentrations below the LLOQ at any point in the profile will be taken as zero for calculating the AUC. Predose samples that occur before the first drug administration will be assigned a time of 0 hours, as if the sample had been taken simultaneously with the study drug administration.

The Phoenix WinNonlin NCA Core Output will be provided in a separate listing.

### 16.1.2.2 Urine and Feces

Urine and fecal parameters for M5717 and/or metabolites, if calculated, will be reported in a separate report.

# 16.1.3 Statistical Summary and Analysis

For Parts A and C, whole blood PK parameters (as described in Section 16.1.2.1) will be calculated, if estimable, using actual elapsed times and noncompartmental methods, PPD PPD

All statistical analyses and descriptive summaries of PK concentrations and PK parameters will be performed on the PK Analysis Set. Any PK concentrations or PK parameters excluded from the PK Analysis Set will be listed and flagged.

Pharmacokinetic concentrations will be reported and analyzed with the same precision as the source data provided by the bioanalytical laboratory or clinical laboratory. Actual elapsed sample collection times will be analyzed unrounded (maximum of 14 significant digits), but will be rounded to two decimal places with units of hours for reporting purposes in by-subject listings.

Pharmacokinetic parameters will be analyzed unrounded, but will be rounded to 3 significant digits for reporting, except for parameters directly obtained from the source data (such as Cmax) which will be reported with the same precision as the source data, and tmax which will be reported to 2 decimal places. In export datasets, as well as in the SDTM PP/XD domain, PK/PD parameters will be provided with full precision, and will not be rounded.

# Presentation of PK Blood Concentrations

M5717 PK whole blood concentration data including dried blood spot assay concentrations will be descriptively summarized using: number of non-missing observations (N), arithmetic mean (Mean), SD, coefficient of variation (CV%), Min, Median, and Max.

Descriptive statistics of whole blood concentration data including dried blood spot assay concentrations will be calculated using values with the same precision as the source data, and rounded for reporting purposes only. The following PK conventions will be applied when reporting descriptive statistics:

Mean, Min, Median, Max. 3 significant digits

SD: 4 significant digits

CV%: 1 decimal place

### Presentation of PK Parameters

Calculated PK parameters will be descriptively summarized using: N, Mean, SD, CV%, Min, Median, Max, geometric mean (GeoMean), the geometric coefficient of variation (GeoCV%) and the lower and upper bounds of the 95% confidence interval (CI) for the GeoMean (LCI 95% GM, UCI 95% GM). GeoMean, GeoCV, LCI 95% GM, and UCI 95% GM will not be presented for tmax.

Descriptive statistics of PK parameter data will be calculated using full precision values, and rounded for reporting purposes only.

The following conventions will be applied when reporting descriptive statistics of PK parameter data, except for tmax which will use the same level of decimal precision (instead of significant digits) as specified below:

Means, Min, Median, Max, GeoMean, 95% CI: 3 significant digits

4 significant digits SD:

1 decimal place CV%, GeoCV%:

Document No. Object No. CC

# Statistical Analysis

All PK whole blood concentrations including dried blood spot assay concentrations, and whole blood PK parameters will be descriptively summarized by trial part, analyte, and dose group as described above. A listing of PK blood sample collection times as well as derived sampling time deviations will also be provided.

PK urine and fecal sample collection start and stop times, and urine volumes and fecal weights will be listed.

Individual whole blood concentration-time profiles by trial part, analyte, and dose group will be created using the actual time points and the numeric concentration data. These figures will include plots of all subjects in the same dose group on the same plot (spaghetti plots), as well as separate plots for individual subjects (by-subject plots). Arithmetic mean whole blood concentration-time profiles by trial part, analyte, and dose group will be provided using nominal time points and the numeric concentration data. All concentration-time plots for PK data will be presented both on a linear and on a semi-logarithmic scale. Mean plots will include SD error bars when plotted on a linear scale.

Linear scatter plots of individual and geometric mean values of non-normalized and dosenormalized parameters [AUC0-∞, AUC0-1, AUC0-144h, and Cmax] versus M5717 dose (on continuous scale) will be prepared, as appropriate. Box plots of the dose-normalized parameters versus M5717 dose (on continuous scale) will be prepared. When applicable, parameters from Part A and Part C will be combined on the same plot (for scatter plots, different symbols will be used for data from the different study parts). Otherwise, plots will be prepared separately by trial part, as applicable.

The analysis of dose proportionality of single-dose PK parameters of M5717 will be quantified as part of an exploratory analysis using the power model on the original parameters (ln[PK parameter]=  $\alpha + \beta \times \ln[\text{dose}]$ ). This analysis will be based on AUC0-\infty, AUC0-1, AUC0-144h, and Cmax in Part A and Part C. The intercept  $\alpha$  and the slope  $\beta$  together with 90% CIs will be estimated and presented. A p-value testing whether  $\beta = 1$  will also be presented. For a given parameter, a minimum of 3 values must be available for a dose level, for that dose level to be included in the dose proportionality analysis.

A listing of the PK blood sample collection times for the DBS assay (for samples collected from subjects in Cohorts 1 and 2 of Part C) as well as derived sampling time deviations will be provided. A correlation analysis of DBS concentrations versus corresponding whole blood concentrations measured at the same nominal time will be performed. The concentration data will be log-transformed for the analysis. The estimate for correlation coefficient (r) and p-value testing whether r = 0 will be presented.

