5.2.5 Rescue Medication for Breakthrough Infections

Subjects in Part C will be prescribed an approved regimen for curative therapy for malaria, to assure final parasite clearance, at recrudescence or at the end of the trial. All subjects will receive Riamet; in addition, Primacin 45 mg will be administered to those subjects who have evidence of gametocytemia. *P. falciparum* 3D7, the parasite strain constituting the inoculum, is fully sensitive to both Riamet and Primacin. Loss of sensitivity is regularly checked in vitro.

The curative/rescue drugs will be inventoried prior to the beginning of trial enrollment on trial accountability logs, to document condition upon receipt, including lot numbers. The Investigator or qualified trial personnel designated by the Investigator will ensure that the received drugs are the specified formulation. The trial site Pharmacist or a nominee designated by the Investigator is

responsible for maintaining an accurate inventory and accountability record of drug supplies for this trial.

- Riamet (20 mg artemether and 120 mg lumefantrine) oral tablets. A course of treatment comprises 6 doses of 4 tablets each (total course of 24 tablets) given over a period of 60 hours. Four oral tablets are administered as a single-dose, administered twice daily at 12 hour intervals, ie, time 0, 12 hours, 24 hours, 36 hours, 48 hours, and 60 hours. Each dose of tablets administered orally should be consumed with food
- Primacin (7.5 mg primaquine phosphate) oral tablets: To clear gametocytes of *P. falciparum*, subjects will receive 45 mg as a single dose with food at the end of their Riamet treatment if gametocytes are identified by gametocyte-specific PCR.

Compulsory commencement of clearance medication will occur no later than 21 days after the last dose of M5717. Administration of rescue medications prior to Day 22 will be determined at the Investigator's discretion using the following criteria:

- Failure of clearance: defined as failure to clear parasitemia by at least 10-fold at 72 hours post IMP administration
- Recrudescence: defined as ≥ 5000 blood stage parasites/mL and a 2-fold parasitemia increase within 48 hours, or re-occurrence of malaria symptoms with a malaria clinical score > 6 .

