8.5.2.2 Pharmacokinetics

Part C

All PK blood concentrations and PK parameters will be descriptively summarized by trial part, dose level, trial day, and/or nominal time point, as described in Section 8.5.1. For calculation of descriptive statistics of blood concentrations, values below the LLOQ will be set to zero.

The statistical analysis of dose proportionality (and the statistical analysis of linearity and accumulation, if applicable, depending on the trial design of Part C) that is described in Section 8.5.3.1, will be repeated after including applicable PK parameters from Part C.

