# 9 General Specifications for Data Analyses

Data will generally be presented separately for each part (Part A or Part C) of the study, although some combination of data across parts may be done, where appropriate (see Section 16.1.3).

Details on PK and PD data presentation can be found in Section 16.

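### The dose-proportionality power model uses Part A and Part C data without a study-part term, so an exposure difference between parts, if there is one, could be read partly as non-proportionality

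*SAP*

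**What the plan says.** SAP 16.1.3 (Statistical Analysis) says: "The analysis of dose proportionality of single-dose PK parameters of M5717 will be quantified as part of an exploratory analysis using the power model". It gives a two-parameter power model for AUC0-∞, AUC0-t, AUC0-144h and Cmax, and names both Part A and Part C as the source of the data. Intercept and slope "together with 90% CIs will be estimated and presented", with a p-value for β = 1. No study-part term appears, and SAP section 7 (changes to the planned analyses) adds none.

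The SAP sentence does not use the word pooled, but two other places make pooling the natural reading:
- Protocol 8.5.2.2 says that the dose-proportionality analysis "will be repeated after including applicable PK parameters from Part C".
- SAP section 9 says that "some combination of data across parts may be done, where appropriate (see Section 16.1.3".

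The SAP does distinguish the parts graphically: "for scatter plots, different symbols will be used for data from the different study parts".

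On rescue in Part C, Protocol 5.2.5 states that "All subjects will receive Riamet", starting no later than 21 days after the last M5717 dose. PK sampling runs to 1032 h (Protocol Table 3).

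**The concern.** Part A and Part C differ in more than dose. Part C subjects are parasitemic when dosed and all later receive artemether/lumefantrine. Their doses are chosen for the parasite response, not to spread evenly over the Part A range. Protocol 5.2.2 updates the predicted efficacious dose to 600 to 800 mg, in the upper part of that range. Part C doses near there would make study part correlated with ln(dose). A model without a part term would then assign some of any between-part exposure difference to β. The slope, its 90% CI and the p-value for β = 1 would mix dose proportionality with a comparison of two different groups of subjects.

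**Working it through.** The documents give no CV, alpha or power for dose proportionality, so there is no planned figure to reproduce. The check uses the algebra for an omitted variable in least squares.

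**Inputs from the documents**
- Part A: 6 active subjects per cohort (Protocol 5.2.2). Doses 50, 100, 200, 400, 600, 1,000 and 1,250 mg, taking one of the two lower sequences that Protocol 5.2.2 offers. This gives 7 × 6 = 42 subjects.
- Part C: up to 3 cohorts of 8, all active (Protocol 5.2.4), so 24 subjects.

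**Assumptions not in the documents**
- The Part C doses.
- The Part C/Part A exposure ratio R, taken as constant over dose.
- A CV of 40%, so σ = √ln(1 + 0.4²) = 0.385.

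**Formulas**, with x = ln(dose) and d = mean x in Part C minus mean x in Part A:
- Sxp = (42 × 24 / 66) × d = 15.27 × d
- Sxx = Sxx(A) + Sxx(C) + 15.27 × d²
- Bias in β without a part term = ln(R) × Sxp / Sxx
- SE(β) without a part term = σ / √Sxx; with it, σ / √(Sxx(A) + Sxx(C))

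**Worked case, Part C at 600/800/1,000 mg**
- Mean x is 5.749 in Part A (geometric mean 314 mg) and 6.663 in Part C, so d = 0.914.
- Sxp = 15.27 × 0.914 = 13.96.
- Sxx = 51.70 + 1.05 + 12.76 = 65.51, so Sxp/Sxx = 0.213.
- Bias at R = 0.7: ln(0.7) × 0.213 = -0.357 × 0.213 = -0.076.
- SE(β) without the term: 0.385/√65.51 = 0.048. The 90% half-width is 1.669 × 0.0476 = 0.079.
- SE(β) with the term: 0.385/√52.75 = 0.053, which is 11% larger.

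| Part C doses (mg) | Bias, R = 0.7 | Bias, R = 0.9 | 90% half-width, no part term | SE(β) without → with part term |
|---|---|---|---|---|
| 600/800/1,000 | -0.076 | -0.022 | 0.079 | 0.048 → 0.053 |
| 400/600/800 | -0.056 | -0.017 | 0.084 | 0.050 → 0.053 |
| 100/200/400 | +0.039 | +0.012 | 0.081 | 0.049 → 0.050 |
| 150/300/600 | +0.004 | +0.001 | 0.083 | 0.050 → 0.050 |

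The half-widths hold σ at 0.385 and ignore the small inflation of residual variance when R differs from 1.

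**Sensitivity to the assumed doses.** Part C doses at the ends of the range give more: 800/1,000/1,250 mg gives about -0.087 and 50/100/200 mg about +0.079 at R = 0.7. With nine Part A doses (300 and 1,500 mg added), Part C at 600/700/800 mg gives 0.052 in size, against 0.070 with seven. At R = 1 the bias is zero everywhere.

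**Effect on the p-value.** In 20,000 simulated trials with true β = 1, seven Part A doses, Part C at 600/700/800 mg and R = 0.70 or 1.43, a two-sided 0.10 test rejected β = 1 in 49 to 50% of trials at CV 30% and in 28 to 29% at CV 50%. With the part term the rate returned to about 10%. The SAP states no alpha, so 0.10 is chosen here to match the 90% CI.

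**Rescue timing.** The latest start is 21 × 24 = 504 h after the last dose. AUC0-144h, and normally Cmax, are complete by then. Compulsory rescue can therefore bear only on AUC0-t and AUC0-∞. Protocol 5.2.5 allows earlier rescue, including for failure of clearance assessed at 72 h, and that could precede 144 h.

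**The case against.** The case for leaving the plan alone has real weight:

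- **No between-part difference is shown.** The documents do not say that infection or rescue changes M5717 exposure. A reader might infer that an infection effect will appear as non-proportionality. That needs both a real difference and off-centre Part C doses, and the documents establish neither. This stands, and the point is conditional for that reason.
- **The whole difference does not go into β.** It is split among intercept, slope and residual. In the worked case about a fifth (0.213 of ln R) reaches the slope, and for centred doses almost none does. This stands.
- **A Part A-only fit is implied.** Protocol 8.5.2.2 speaks of repeating the analysis with Part C added, so a fit without Part C should come first. This stands, but the SAP does not restate it.
- **The parts can be compared elsewhere.** A reader might infer that the trial has no other view of exposure in infected against healthy subjects. The SAP summarises dose-normalised parameters by trial part and dose group, plots both parts together where applicable, and plans a separate population PK analysis with covariates. The comparison is not lost. None of these outputs is specified as a dose-adjusted between-part ratio with an interval.
- **Whole-blood assay does not separate the parts.** M5717 is measured in whole blood in both.
- **The analysis is exploratory.** Protocol 8.5.1 rules out formal hypothesis testing, no alpha or decision rule attaches to β, and dose decisions rest with the SMC. This limits the severity.
- **Protocol 8.5.3.1 is partly redacted**, so a part term there cannot be excluded. The SAP formula itself is printed in full and has none.

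**Conclusion.** The point holds conditionally and is minor. As printed, the SAP model cannot separate a dose effect from a study-part effect when Part C doses are off-centre. Under the stated assumptions, and for the dose sets in the table, an exposure ratio of 0.7 biases β by about -0.08 to +0.04. The largest of these is about the size of the 90% CI half-width (0.08). A ratio of 0.9 gives at most about 0.02, and Part C doses centred near 300 mg give almost nothing at either ratio. These figures rest on assumed Part C doses, exposure ratios and CV. The documents do not support a claim that β will be biased, that infection alters exposure, or that rescue affects all four modelled parameters.

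**What to change.** In SAP 16.1.3:

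1. State the Part A-only power model as the first fit, in line with Protocol 8.5.2.2.
2. Fit the combined data as ln(parameter) = α + β × ln(dose) + γ × Part, as a supportive analysis.
3. Report β and exp(γ), each with a 90% CI. Describe exp(γ) as a non-randomised between-part exposure ratio, not as an infection effect.

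The cost is one degree of freedom and an SE of β up to about 11% larger for the dose sets in the table (more if Part C doses sit at the ends of the range). The part term removes the bias if the ratio is constant over dose. In the worked case, SE(γ) = 0.385/√(15.27 - 13.96²/65.51) = 0.110, so the 90% CI for exp(γ) would run from the estimate divided by about 1.20 to the estimate multiplied by about 1.20. No new data are needed.

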Part C is a single-center, open-label trial using the *P. falciparum* IBSM human challenge to assess the antimalarial activity of M5717 in healthy subjects infected with malaria under controlled conditions. The trial is planned to be conducted in up to 3 cohorts (n=8 per cohort). A key assumption on which the dose for the first cohort will be selected is that the MPC and MIC value derived from the preclinical severe combined immunodeficient (SCID) mouse efficacy model would be the same in humans, taking into account the observed profile in the human PK data as observed in Part A. The current objective is that the dose of M5717 that will be investigated in the first cohort is a single dose that is expected to lead to levels above the MPC for 8 days. The dose will be estimated using noncompartmental PK analysis. This dose needs to be endorsed by the SMC. Depending on whether the assumed MPC in humans is correct, as well as the extent of parasite reduction observed in the first cohort in this part of the trial, the doses needed to characterize the exposure-response relationship (including doses

leading to recrudescence) will be further refined and decided by the SMC. These dose(s) could be higher or lower than the initially administered dose. Depending on the selected doses, the respective number and strength of capsules will be calculated and administered as specified in the pharmacy manual.

A third cohort will be investigated to further refine and characterize the MIC depending on the level of precision and confidence of the observations in the first 2 cohorts, unless the SMC decides otherwise. Similar scenarios as described for the initial 2 cohorts will be considered for the third cohort, with an alternative dosing time point if deemed necessary, with the intention to further refine the modeling and the Phase II dose predictions.

A maximum of 3 cohorts will be investigated as a single-dose or multiple-dose evaluation in Part C of the trial. The highest dose to be investigated in Part C will not exceed the highest dose administered in Part A or Part B of the trial.

Subjects will be admitted to the trial site for M5717 administration 9 days post administration of the Inoculum (In D9; Day 1). The parasitemia of all subjects at In D9 is expected to be $\geq 5,000$ parasites/mL. However, subjects can be administered M5717 at any time point before or after In D9 at the Investigators discretion based on parasitemia and/or clinical symptoms.

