- d A standard full physical examination, including examination of all body systems, will be performed at Screening and the End of Trial visit (Day 44 ± 2 days), including general appearance, skin, head, neck (including thyroid), eyes, ears, nose, throat, cardiovascular and pulmonary system, abdomen, neurological, peripheral vascular, and musculoskeletal system. At other time points an abbreviated physical examination must be performed. Additional physical examinations may be performed as deemed necessary, per the Investigator's discretion.
- e IMP administration on Day 2 and Day 3 in case Part C will be evaluated with multiple doses based on PK data from Part A and B.
- f Diary cards will be provided to subjects for collection of data relating to their daily physical activity, daily use of sunscreen/other methods of sun protection, daily alcohol consumption, and if applicable, their oral (sublingual) temperature. Subjects will bring their completed diary cards with them to the trial site for all ambulant, Follow-up, and End of Trial visits.

- g Only hematology, coagulation, and urinalysis (dipstick).
- h Coagulation not required on Day 7, Day 9, and Day 15.
- i Samples will be collected and analyzed for the detection of seroconversion against some rare blood stage pathogens or red blood cell antibodies.
- j On Day 1, a time window of 60 minutes is allowed for blood pressure measurements.
- k Vital signs assessments prior to administration of malaria inoculum (In D1) as well as 1 hour post inoculation (In D1).
- l In case the subject is unable to stand up at the 16 hours postdose time point due to dizziness, the vital signs may be assessed in the supine position.

CCI

- q At visits where assessment time points coincide with each other, the following procedure should be followed: perform vital signs assessments slightly before the specific time point, ECG assessments on time, PK blood sampling directly following ECG. Use of agreed upon time windows will be allowed (specified in [Table 4](#)).
- r Including dried blood spot assessments at alternate samples (predose, 1, 2, 6, 10, 16, 24, 36, 48, 96, 144, 240, 504, and 1032 hours).
- s In case Part C will be evaluated with multiple doses based on PK data from Part A and B, PK samples are to be collected predose on IMP administration days (at 24 hours on Day 2 and at 48 hours on Day 3).

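### The planned DBS versus whole-blood correlation with a test of r = 0 cannot show whether the two assays give the same concentration; a paired ratio would, at almost no cost

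*SAP*

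**What the plan says.** SAP Section 7 lists a DBS versus whole-blood correlation among the changes to the protocol's planned analyses. Section 16.1.3 (Statistical Analysis) describes it: "A correlation analysis of DBS concentrations versus corresponding whole blood concentrations measured at the same nominal time will be performed". On scale it says "The concentration data will be log-transformed for the analysis", and on output "The estimate for correlation coefficient (r) and p-value testing whether r = 0 will be presented". It names no mean ratio, slope, intercept, limits of agreement or confidence interval.

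The listing of DBS sampling times is "for samples collected from subjects in Cohorts 1 and 2 of Part C". Protocol Section 5.2.4 sets cohort size: "The trial is planned to be conducted in up to 3 cohorts (n=8 per cohort". Protocol Table 3, footnote r, gives the DBS schedule: "Including dried blood spot assessments at alternate samples (predose, 1, 2, 6, 10, 16, 24, 36, 48, 96, 144, 240, 504, and 1032 hours".

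Two other SAP provisions bear on this:

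- Section 16.1.3 also plans descriptive summaries of both the whole-blood and the DBS concentrations, split by part of the trial and dose. Section 9 sets summaries by nominal time point as appropriate.
- Section 16.1.1.2 gives a rule for values below the limit of quantification: "Concentration values below the LLOQ of the assay will be taken as zero for summary statistics of DBS PK concentration data". It does not say what happens to such values, or to predose samples, in the log-scale correlation.

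**The concern.** When two assays measure the same drug in the same subjects at the same times, a reader wants to know whether they give the same concentration and, if not, by how much they differ. Correlation measures how closely the log values follow a straight line. It does not measure whether that line is the line of equality. The null r = 0 asks only whether there is any linear association, which is hardly in doubt when both series rise and fall with the same drug.

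The plan is also silent on how serial pairs from one subject enter the calculation. What is at stake is the usefulness of the DBS result: as planned, the only paired output would look the same for an accurate assay and for one wrong by a factor of two.

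**Working it through.** The plan gives no sample size, acceptance limit or expected value for this comparison, so there is no figure to reproduce.

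**Inputs from the documents.** Two Part C cohorts of 8 give 2 × 8 = 16 subjects. Footnote r lists 14 times, 13 of them postdose. The maximum is 16 × 13 = 208 postdose pairs (16 × 14 = 224 with predose).

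**1. Bias and r (algebra; no assumed figures).** Let x = log(whole blood) and y = log(DBS). If DBS is multiplied by a constant k, y becomes y + log k. Covariance and standard deviations do not change when a constant is added, so r = cov(x, y)/(SD_x × SD_y) does not change, whether k is 0.5, 1 or 2. Likewise, if the whole DBS reading is raised to a positive power, y is multiplied by a positive constant and r is again unchanged.

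**2. Illustration (assumed pharmacokinetics).** 16 subjects × 13 postdose times; one-compartment profile; half-life about 150 h; 40% between-subject SD; two dose levels. The ratio is the geometric mean of DBS/whole blood, with its 95% confidence interval (CI) from subject means.

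| Assay error | True DBS/whole blood | r | Geometric mean ratio (95% CI) |
|---|---|---|---|
| 15% | 1 | 0.995 | 0.98 (0.97–1.00) |
| 15% | 0.5 | 0.995 | 0.49 (0.49–0.50) |
| 15% | 2 | 0.995 | 1.97 (1.94–1.99) |
| 30% | 1 | 0.981 | 1.02 (0.98–1.05) |
| 30% | 0.5 | 0.981 | 0.51 (0.49–0.53) |
| 30% | 2 | 0.981 | 2.03 (1.97–2.11) |

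The size of r depends on the assumed profile and noise. That it stays the same down each block does not.

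**3. The null r = 0.** The smallest |r| significant at two-sided 0.05 (level assumed; the SAP gives none) is t/√(n − 2 + t²), with t the 97.5% point on n − 2 degrees of freedom. For n = 208 this is 0.136; for n = 224 it is 0.131. As a stress test, whole-blood profiles were paired with DBS profiles simulated for different subjects, with 30% error. Mean r was still 0.77, and p < 0.05 occurred in all 2000 runs, because every profile shares the same time course. Rejection therefore says almost nothing about the assay.

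**4. Repeated samples.** If all 208 pairs were pooled as independent, a Fisher 95% CI for r = 0.95 would be tanh(atanh 0.95 ± 1.96/√205) = 0.935 to 0.962. Counting only the 16 subjects, it is tanh(atanh 0.95 ± 1.96/√13) = 0.859 to 0.983. These are two extremes, and the true precision lies in between. Neither interval is near zero, so within-subject correlation matters for stated precision far more than for rejecting r = 0.

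**The case against.** The best reply is that the plan promises only a correlation and delivers one. Three stronger readings are tempting, and the documents do not support them.

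- *That the result will decide whether DBS can replace venous sampling, and that the plan would declare success for a biased assay.* No visible text states a bridging aim, an acceptance limit or a success rule. Parts of the sampling, objectives and endpoints text are blacked out, so an aim may exist there, but none can be assumed.
- *That the SAP treats the pairs as independent.* It does not say so. Pooling is one reading of a single r with a single p-value; a separate r at each time point is not ruled out. Even at n = 16, r = 0.97 gives t = 0.97 × √14/√(1 − 0.97²) ≈ 14.9, so the conclusion on r = 0 would not change.
- *That a two-fold bias would go unseen.* The same subjects are sampled at the same nominal times, so by-time-point summaries of the two assays could show halved means and medians.

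It is also fair that whole-blood concentrations supply the PK parameters, that DBS appears in no visible endpoint, and that Protocol Section 8.5.1 calls the trial exploratory with no formal hypothesis testing.

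All of this limits the weight of the point. It does not rescue the method. Side-by-side summaries give neither a paired estimate nor its precision, and the one paired analysis cannot register a proportional error of any size. The absence of formal testing is, if anything, a reason to drop the p-value.

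**Conclusion.** The point stands as a minor one. The planned correlation cannot show whether DBS and whole blood give the same concentration. A constant proportional bias of any size leaves r exactly unchanged; this is algebra and rests on no assumption. The test of r = 0 is uninformative for two assays of one drug over 1 to 1032 h: the 0.136 threshold needs 208 pooled pairs, and the simulated values need the pharmacokinetic and error assumptions stated above.

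The handling of up to 13 postdose pairs per subject is unspecified, not shown to be wrong. If they were pooled in a standard test, within-subject correlation would be ignored, with consequences mainly for any confidence interval. No stated endpoint or decision in the visible text depends on this analysis.

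**What to change.** In SAP Section 16.1.3, replace the test with a paired analysis of d = log(DBS/whole blood):

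- Fit d_ij = μ + b_i + e_ij, with a random subject effect b_i. Report exp(μ) as the geometric mean ratio with its 95% CI, and 95% limits of agreement exp(μ ± 1.96 × √(between-subject variance + within-subject variance)).
- Use postdose pairs quantifiable in both assays, and report how many pairs are left out and why. This also removes the undefined log of zero.
- Plot the ratio against concentration, to show whether any bias varies over the range.
- Drop the p-value for r = 0; r may stay as description.

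The cost is a few lines of SAP text, one mixed model and one figure. It needs no new samples and changes no other analysis.
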